7.1.5.5 Second Course Phase (Retreatment Period)

All subjects who stop study treatment with SD or better may be eligible for up to one year of additional pembrolizumab treatment if they progress after stopping study treatment from the initial treatment phase. This retreatment is termed the Second Course Phase of this study and is only available if the study remains open and the subject meets the following conditions:

- **Either**

- Stopped initial treatment with study treatment after attaining an investigator-determined confirmed CR according to RECIST 1.1, and
 - Was treated for at least 8 administrations with study treatment before discontinuing treatment.
 - Received at least 2 treatments with pembrolizumab beyond the date when the initial CR was declared.

OR

- Had SD, PR or CR and stopped study treatment after completion of 35 administrations of pembrolizumab (approximately 2 years) of study treatment for reasons other than disease progression or intolerability.

AND

- Experienced an investigator-determined radiographic disease progression after stopping their initial treatment.
- Did not receive any anti-cancer treatment since the last dose of study treatment.
- Has a performance status of 0 or 1 on the ECOG Performance Scale within 3 days prior to the first dose of trial treatment.
- Demonstrates adequate organ function as detailed in Section 5.1.2. Laboratory tests are to be performed within 3 days prior to the first dose of trial treatment.
- Female subject of childbearing potential should have a negative serum or urine pregnancy test within 72 hours prior to receiving retreatment with study medication.
- Female subject of childbearing potential should be willing to use 2 methods of birth control or be surgically sterile, or abstain from heterosexual activity for the course of the study through 120 or 180 days after the last dose of study medication (Section 5.7.2). Duration of use of contraceptives will depend on which cohort a subject is assigned. Subjects of child bearing potential are those who have not been surgically sterilized or have been free from menses for > 1 year.
- Male subject should agree to use an adequate method of contraception starting with the first dose of study treatment through 120 or 180 days after the last dose of study treatment (Section 5.7.2). Duration of use of contraceptives will depend on which cohort a subject is assigned.

- Does not have a history or current evidence of any condition, therapy, or laboratory abnormality that might interfere with the subject's participation for the full duration of the trial or is not in the best interest of the subject to participate, in the opinion of the treating investigator.

Subjects who restart treatment will be retreated at the same dose and dose interval as when they last received pembrolizumab. Treatment will be administered for up to one additional year.

Visit requirements are outlined in Section 6.0 – Trial Flow Chart.

7.1.5.6 Survival Status

To ensure current and complete survival data are available at the time of database locks, updated survival status may be requested during the course of the study by the Sponsor. For example, updated survival status may be requested prior to but not limited to an external Data Monitoring Committee review, interim and/or final analysis. Upon Sponsor notification, all participants who do not/will not have a scheduled study visit or study contact during the Sponsor-defined time period will be contacted for their survival status (excluding participants that have previously recorded a death event in the collection tool).

7.2 Assessing and Recording Adverse Events

An adverse event is defined as any untoward medical occurrence in a patient or clinical investigation subject administered a pharmaceutical product and which does not necessarily have to have a causal relationship with this treatment. An adverse event can therefore be any unfavourable and unintended sign (including an abnormal laboratory finding, for example), symptom, or disease temporally associated with the use of a medicinal product or protocol-specified procedure, whether or not considered related to the medicinal product or protocol-specified procedure. Any worsening (i.e., any clinically significant adverse change in frequency and/or intensity) of a preexisting condition that is temporally associated with the use of the Sponsor's product, is also an adverse event.

Changes resulting from normal growth and development that do not vary significantly in frequency or severity from expected levels are not to be considered adverse events. Examples of this may include, but are not limited to, teething, typical crying in infants and children and onset of menses or menopause occurring at a physiologically appropriate time.

Sponsor's product includes any pharmaceutical product, biological product, device, diagnostic agent or protocol-specified procedure, whether investigational (including placebo or active comparator medication) or marketed, manufactured by, licensed by, provided by or distributed by the Sponsor for human use.

Adverse events may occur during clinical trials, or as prescribed in clinical practice, from overdose (whether accidental or intentional), from abuse and from withdrawal.

Progression of the cancer under study is not considered an adverse event.

All adverse events that occur after the consent form is signed but before randomization/treatment allocation must be reported by the investigator if they cause the subject to be excluded from the trial, or are the result of a protocol-specified intervention, including but not limited to washout or discontinuation of usual therapy, diet, placebo treatment or a procedure.

From the time of randomization/treatment allocation through 30 days following cessation of treatment, all adverse events must be reported by the investigator. Such events will be recorded at each examination on the Adverse Event case report forms/worksheets. The reporting timeframe for adverse events meeting any serious criteria is described in section 7.2.3.1. The investigator will make every attempt to follow all subjects with non-serious adverse events for outcome.

Electronic reporting procedures can be found in the EDC data entry guidelines. Paper reporting procedures can be found in the Investigator Trial File Binder (or equivalent)..

7.2.1 Definition of an Overdose for This Protocol and Reporting of Overdose to the Sponsor

For this trial, an overdose of:

- pembrolizumab will be defined as any dose of 1,000 mg or greater (≥ 5 times the indicated dose)
- any standard treatment is any dose $\geq 20\%$ over the prescribed dose.

No specific information is available on the treatment of overdose of pembrolizumab. In the event of overdose, the subject should be observed closely for signs of toxicity. Appropriate supportive treatment should be provided if clinically indicated.

Overdoses of cisplatin, 5-FU and capecitabine (Japan only), will be managed in accordance with the respective product label.

If an adverse event(s) is associated with (“results from”) the overdose of Sponsor's product or vaccine, the adverse event(s) is reported as a serious adverse event, even if no other seriousness criteria are met.

If a dose of Sponsor's product or vaccine meeting the protocol definition of overdose is taken without any associated clinical symptoms or abnormal laboratory results, the overdose is reported as a non-serious Event of Clinical Interest (ECI), using the terminology “accidental or intentional overdose without adverse effect.”

All reports of overdose with and without an adverse event must be reported within 24 hours to the Sponsor either by electronic media or paper. Sponsor Contact information can be found in the Investigator Trial File Binder (or equivalent).

7.2.2 Reporting of Pregnancy and Lactation to the Sponsor

Although pregnancy and lactation are not considered adverse events, it is the responsibility of investigators or their designees to report any pregnancy or lactation in a subject (spontaneously reported to them) that occurs during the trial.

Pregnancies and lactations that occur after the consent form is signed but before randomization/treatment allocation must be reported by the investigator if they cause the subject to be excluded from the trial, or are the result of a protocol-specified intervention, including but not limited to washout or discontinuation of usual therapy, diet, placebo treatment or a procedure.

Pregnancies and lactations that occur from the time of randomization/treatment allocation through 120 days following cessation of Sponsor's product, or 30 days following cessation of treatment if the subject initiates new anticancer therapy, whichever is earlier, must be reported by the investigator. All reported pregnancies must be followed to the completion/termination of the pregnancy. Pregnancy outcomes of spontaneous abortion, missed abortion, benign hydatidiform mole, blighted ovum, fetal death, intrauterine death, miscarriage and stillbirth must be reported as serious events (Important Medical Events). If the pregnancy continues to term, the outcome (health of infant) must also be reported.

Such events must be reported within 24 hours to the Sponsor either by electronic media or paper. Electronic reporting procedures can be found in the EDC data entry guidelines. Paper reporting procedures can be found in the Investigator Trial File Binder (or equivalent).

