10. Have measurable disease based on RECIST 1.1 as determined by central imaging vendor. Tumor lesions situated in a previously irradiated area are considered measurable if progression has been demonstrated in such lesions.
- a. *Note: The exact same image acquisition and processing parameters should be used throughout the study.*
11. Have a performance status of 0 or 1 on the ECOG Performance Scale (Appendix 12.4) within 3 days prior to the first dose of study therapy.
12. Life expectancy of at least 3 months.
13. Female subjects of childbearing potential should be willing to use 2 methods of birth control or be surgically sterile, or abstain from heterosexual activity for the course of the study through 120 or 180 days after the last dose of study medication (Section 5.7.2). Duration of use will be determined when the subject is assigned to treatment. Subjects of childbearing potential are those who have not been surgically sterilized or have not been free from menses for > 1 year.
- Male subjects should agree to use an adequate method of contraception starting with the first dose of study therapy through 120 or 180 days after the last dose of study therapy. Duration will be determined when the subject is assigned to treatment.
- Abstinence is acceptable if this is the usual lifestyle and preferred contraception for the subject.
14. Demonstrate adequate organ function as defined in [Table 1](#). All screening labs should be performed within 3 days prior to treatment initiation.

Table 1 Adequate Organ Function Laboratory Values

System	Laboratory Value
Hematological	
Absolute neutrophil count (ANC)	$\geq 1,500/\text{mcL}$
Platelets	$\geq 100,000/\text{mcL}$
Hemoglobin	$\geq 9 \text{ g/dL}$ or $\geq 5.6 \text{ mmol/L}$ without transfusion or EPO dependency (within 7 days of assessment)
Renal	
Creatinine OR Measured or calculated creatinine clearance (GFR can also be used in place of creatinine or CrCl)	$\leq 1.5 \text{ X}$ upper limit of normal (ULN) OR $\geq 60 \text{ mL/min}$ for subject with creatinine levels $> 1.5 \text{ X}$ institutional ULN Cisplatin product label should be followed for acceptable creatinine clearance rates for subjects in Cohort 2 (combination treatment) Notes: Creatinine clearance should be calculated per institutional standard.
Hepatic	
Total bilirubin	$\leq 1.0 \text{ X ULN}$
AST (SGOT) and ALT (SGPT)	$\leq 2.5 \text{ X ULN}$ OR $\leq 5 \text{ X ULN}$ for subjects with liver metastases
Albumin	$\geq 3.0 \text{ g/dL}$

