9. Has known active central nervous system (CNS) metastases and/or carcinomatous meningitis. Subjects with previously treated brain metastases may participate provided they are stable (without evidence of progression by imaging at least four weeks prior to the first dose of trial treatment and any neurologic symptoms have returned to baseline), have no evidence of new or enlarging brain metastases, and are not using steroids for at least 7 days prior to trial treatment. This exception does not include carcinomatous meningitis which is excluded regardless of clinical stability.
10. Has history of (non-infectious) pneumonitis that required steroids or has current pneumonitis.
11. Has an active infection requiring systemic therapy.
12. Has a history or current evidence of a gastrointestinal (GI) condition (e.g., inflammatory bowel disease, Crohn's disease, ulcerative colitis) or impaired liver function or diseases that in the opinion of the Investigator may significantly alter the absorption or metabolism of oral medications; any condition (e.g., known deficiency of the enzyme dihydropyrimidine dehydrogenase), therapy, or laboratory abnormality that might confound the results of the study, interfere with the participant's participation for the full duration of the study, make administration of the study drugs hazardous, or make it difficult to monitor adverse effects such that it is not in the best interest of the subject to participate (e.g., any contraindication to the use of cisplatin, 5-FU, or capecitabine for subjects in Japan, in the opinion of the treating investigator).
13. Has known psychiatric or substance abuse disorders that would interfere with cooperation with the requirements of the trial.

14. Is pregnant or breastfeeding or expecting to conceive or father children within the projected duration of the trial, starting with the screening visit through 120 or 180 days after the last dose of trial treatment. Duration is determined by the cohort to which the subject would be assigned.
15. Has received prior therapy with an anti-PD-1, anti-PD-L1, or anti-PD-L2 agent.
16. Has a known history of Human Immunodeficiency Virus (HIV) (HIV 1/2 antibodies).
17. Has known chronic or acute Hepatitis B (e.g., HBsAg reactive) or Hepatitis C infection (e.g., HCV RNA [qualitative] is detected).
18. Has received a live vaccine within 30 days of planned start of study therapy.

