5.7.2 Contraception

Pembrolizumab may have adverse effects on a fetus in utero. Furthermore, it is not known if pembrolizumab has transient adverse effects on the composition of sperm. Non-pregnant, non-breast-feeding women may be enrolled if they are willing to use 2 methods of birth control or are considered highly unlikely to conceive. Highly unlikely to conceive is defined as 1) surgically sterilized, or 2) postmenopausal (a woman who is ≥ 45 years of age and has not had menses for greater than 1 year will be considered postmenopausal), or 3) not heterosexually active for the duration of the study. The two birth control methods can either be two barrier methods or a barrier method plus a hormonal method to prevent pregnancy.

Subjects in Cohorts 1 & 3 should start using birth control from study Visit 1 throughout the study period up to 120 days after the last dose of study treatment. Subjects in Cohort 2 should start using birth control from study Visit 1 throughout the study period up to 180 days after the last dose of study treatment.

The following are considered adequate barrier methods of contraception: diaphragm, condom (by the partner), copper intrauterine device, sponge, or spermicide as per local regulations or guidelines. Appropriate hormonal contraceptives will include any registered and marketed contraceptive agent that contains an estrogen and/or a progestational agent (including oral, subcutaneous, intrauterine, or intramuscular agents).

Abstinence is acceptable if this is the usual lifestyle and preferred contraception for the subject.

Subjects should be informed that taking the study medication may involve unknown risks to the fetus (unborn baby) if pregnancy were to occur during the study. In order to participate in the study they must adhere to the contraception requirement (described above) for the duration of the study and during the follow-up period defined in Section 7.2.2 - Reporting of Pregnancy and Lactation to the Sponsor. If there is any question that a subject will not reliably comply with the requirements for contraception, that subject should not be entered into the study.

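### Section 7.2.2 sets a single 120-day pregnancy-reporting window, although Section 5.7.2 runs contraception to 180 days in Cohort 2 and points to 7.2.2 for the follow-up period (minor)

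*Combined protocol and SAP*

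**What the plan says.** Two sections of the protocol set periods after treatment.

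- **Contraception, Section 5.7.2.** Cohorts 1 and 3 continue birth control to 120 days after the last dose. Cohort 2 continues "throughout the study period up to 180 days after the last dose of study treatment". The section then tells subjects that "they must adhere to the contraception requirement (described above) for the duration of the study and during the follow-up period defined in Section 7.2.2".
- **Pregnancy reports, Section 7.2.2.** Investigators must report pregnancies and lactations from allocation "through 120 days following cessation of Sponsor's product". No cohort is named. An earlier stop applies to anyone who moves on to another cancer treatment: "or 30 days following cessation of treatment if the subject initiates new anticancer therapy, whichever is earlier". The section opens with a general duty to "report any pregnancy or lactation in a subject (spontaneously reported to them) that occurs during the trial", which carries no day count.

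The split by cohort is deliberate and recurs elsewhere. Inclusion criterion 13 in Section 5.1.2 gives 120 or 180 days and refers to 5.7.2. Exclusion criterion 14 in Section 5.1.3 gives the same pair and adds: "Duration is determined by the cohort to which the subject would be assigned". The Second Course criteria in Section 7.1.5.5 say: "Duration of use of contraceptives will depend on which cohort a subject is assigned". Of the sections that give a post-treatment period for pregnancy, only 7.2.2 lacks the 180-day figure.

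**The concern.** A contraception period says how long conception is to be avoided because of drug exposure. One expects the mandatory reporting of pregnancies to run at least as long, and Section 5.7.2 expects this too, because it treats 7.2.2 as the definition of the follow-up period. A reader who follows that reference for Cohort 2 finds 120 days instead of 180.

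At stake is the completeness of pregnancy reporting in the combination cohort, whose primary objective is safety. A site working from the dated sentence in 7.2.2 has no explicit instruction that a pregnancy on, say, day 150 must be reported within 24 hours. Nothing in the efficacy or safety analyses of the SAP depends on this.

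**Working it through.** The protocol gives no figure of its own for the gap, so the check is a comparison of the stated periods and a subtraction.

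**Inputs**

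| Item | Value | Source |
|---|---|---|
| Dated reporting window, all cohorts | 120 days from cessation of Sponsor's product | Section 7.2.2 |
| Contraception, Cohorts 1 and 3 | 120 days from last dose | Section 5.7.2 |
| Contraception, Cohort 2 | 180 days from last dose | Section 5.7.2 |
| Planned size of Cohorts 1, 2 and 3 | about 210, 18 and 25 | Sections 2.2 and 8.9 |

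**Gap for subjects who start no new anticancer therapy**

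Gap = contraception period − dated reporting window, with both clocks starting on the same day.

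- Cohorts 1 and 3: 120 − 120 = 0 days. Pembrolizumab is the only agent, so the two clocks coincide.
- Cohort 2: 180 − 120 = 60 days, which is 60/180 = 33% of the contraception period.

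**Starting points.** Section 7.2.2 counts from the end of Sponsor's product and 5.7.2 from the last dose of study treatment. Section 7.1.3.1 foresees Cohort 2 subjects on chemotherapy with or without pembrolizumab. Section 9.1 allows cisplatin and 5-FU to be supplied locally and does not list capecitabine among the Sponsor's supplies. If Sponsor's product stops *d* days before the last study dose, the gap is (180 + *d*) − 120 = 60 + *d* days. The documents give no value for *d*; the 60 days correspond to *d* = 0.

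**Subjects affected.** 210 + 18 + 25 = 253, and 18/253 = 7.1%. This is an upper limit, because only some of the 18 will be able to conceive or father a child and only some will remain free of new anticancer therapy.

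**What covers days 121 to 180 in Cohort 2**

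| Route | Reach |
|---|---|
| Section 7.2.2, opening duty | Applies during the trial, but only to pregnancies the investigator is told of spontaneously |
| Section 5.7.3 | A subject's pregnancy while on treatment; partner pregnancies, with follow-up referred back to 7.2.2 |
| Section 7.2.3.1 | At any time, but only serious adverse events judged related; 7.2.2 says pregnancy itself is not an adverse event |
| Section 7.1.5.4.3, telephone calls | Survival status and later anticancer treatment, after confirmed progression or new therapy; pregnancy is not listed |

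The first route can capture a pregnancy in these 60 days. None of the four replaces a dated mandatory window.

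**After the fix.** Cohort 2: 180 − 180 = 0 days. Counting from the last dose of any study treatment also removes *d*.

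**The case against.** The best defence is that these are two different duties. Section 5.7.2 governs what subjects do and 7.2.2 governs what investigators report, and both can be obeyed as written. Subjects also normally stay in the trial beyond day 120. Section 2.1 keeps them in survival follow-up, and those without progression or new therapy attend imaging visits under Section 7.1.5.4.2, at which the flow chart schedules adverse-event review. A pregnancy in that period would often come to light and fall under the opening duty of 7.2.2. This stands, and it keeps the point small. It does not explain why a section that 5.7.2 cites as defining the follow-up period has the right figure for two cohorts and not for the third.

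Three stronger readings are tempting, and the documents do not support them.

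- *A reader might infer that nothing need be reported after day 120.* The opening sentence of 7.2.2 has no day limit and the dated sentence does not cancel it. The two rules are compatible; the dated one is simply too short for Cohort 2.
- *A reader might infer that Cohort 2 may stop contraception at day 120.* Section 5.7.2 states 180 days expressly and ties adherence to the requirement it has just described. The contraception rule is clear, and that misreading is unlikely.
- *A reader might add the 30-day cut-off after new anticancer therapy to the gap.* That cut-off applies to every cohort, is a separate choice by the sponsor and is untouched by this correction. It is not part of this point.

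**Conclusion.** The inconsistency is real and minor. Section 7.2.2 applies the monotherapy period to all cohorts, so 60 of the 180 days of required contraception in Cohort 2 have no dated mandatory reporting rule and depend on the general duty for spontaneously reported pregnancies.

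The 60 days rest on two conditions: no new anticancer therapy is started, and all agents stop on the same day. If chemotherapy outlasts the Sponsor's product, the gap is longer by an amount the documents do not allow one to state. At most about 18 subjects (7% of the trial) are concerned. The number of childbearing potential is not given, so an expected count of pregnancies cannot be computed and is probably low. No endpoint, estimate, sample size or planned analysis changes. The correction is still worth making because it costs almost nothing and concerns a stated safety-reporting rule.

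**What to change.** Reword the dated sentence in Section 7.2.2 so that mandatory reporting runs from allocation to 120 days in Cohorts 1 and 3 and to 180 days in Cohort 2, counted from the last dose of any study treatment. Leave the opening general duty as it is. The cross-reference in 5.7.2 then becomes correct without further editing, and the wording matches the eligibility criteria and Section 7.1.5.5.

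The cost is one sentence in the protocol, passed on to sites in the reporting instructions. It needs no new visits, tests or scheduled calls. The 30-day cut-off after new anticancer therapy can stay as written.
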